10.3.3.6 Subgroup analyses

Exploratory subgroup analyses are planned for the primary efficacy variable, also the secondary efficacy variables. This will include descriptive statistics and a statistical test for interaction.

The following subgroups will be considered for exploratory subgroup analyses:

- Region (North America, Latin America, Europe, Asia, Others)
- eGFR category at screening and baseline (eGFR 25 to < 45, 45 to < 60 and ≥ 60 mL/min/1.73m²)
- Type of albuminuria at screening and baseline (high albuminuria vs very high albuminuria)
- History of CVD (present, absent)
- Baseline serum potassium (≤ 4.5 vs. > 4.5 mmol/L)
- Systolic blood pressure at baseline (90 to <130 , 130 to <160 and ≥ 160 mmHg).

It is anticipated that in these proposed subgroups for analysis, differences in treatment effects may be observed according to the screening or baseline characteristics defined, due in part to the differences in the risk of clinical events expected in the different subgroups.

Furthermore, subgroup analysis usually required will be performed, including the following subgroups:

- Race
- Gender
- Age group.

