10.4 Determination of sample size - amended

This section was changed in Amendment 3, see Section [15.1.2.41](#).

This is an event-driven study. A total of between 970 and 976 primary efficacy endpoint events will have 90% power to demonstrate superiority of finerenone to placebo using a logrank test at a two-sided significance level of 5.0%, assuming a 20% relative risk reduction, i.e. a true hazard ratio of 0.80 (the hazard ratio that will be observed in the study will be different, i.e. closer to 1 due to treatment discontinuations). The study will stop when approximately 976 primary efficacy endpoints accrue across both treatment arms.

With an assumed treatment duration of between 44 and 48 months (duration of recruitment period: 33 and 41 months, equal recruitment pattern during the accrual period, maximum treatment period of the last subject recruited: 11 and 7 months, respectively), the planned total number of subjects to be randomized is estimated to be between 6212 and 6286 subjects, respectively, assuming an annual placebo event rate of 8%, a common annual lost-to-follow-up rate of 0.7% in both treatment groups, an annual finerenone discontinuation rate of 5% and assuming that placebo discontinuation will not change the hazard. 6400 subjects are planned to be randomized taking a certain ramp-up during recruitment into account. Assuming a screening failure rate of 50%, 12800 subjects are planned to be screened.

Due to the minimal effect of the interim analysis on the overall power of the study, an adjustment of sample size would be negligible.

The assumption of the annual placebo event rate of 8% is based on the results from the MICRO-HOPE, RENAAL, IDNT, ALTITUDE and SAVOR-TIMI 53 trials. The latter 2 are more recent studies. Event rates were obtained from the respective studies in the arms where treatment would more closely resemble that in the placebo population of the CV-DKD study who will be on standard of care treatment for DKD. Annual event rates for the composite CV endpoint range from 7-10% for older studies and 5-6% for more recent studies. As the anticipated population study 17530 will be more enriched for CV outcomes than ALTITUDE and SAVOR-TIMI 53, a likely lower mean eGFR and higher median UACR value, the assumed annual placebo event rate of 8% is assumed to be appropriate for this Phase III setting ([10](#), [11](#), [51-54](#)).

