4.5.4 Subgroup analyses

Exploratory subgroup analysis will be performed for the primary and secondary efficacy variables. The subgroup analyses will include the randomization stratification factors. The list of key subgroups (in addition to the stratification factors) and other subgroups analyzed is specified below. Analysis will include descriptive statistics, graphical display of estimated treatment effects with 95%-CIs in a forest plot and a statistical test for interaction.

Stratification factors:

- Region (North America, Latin America, Europe, Asia, Others)
- eGFR category at screening (eGFR 25 to <45, 45 to <60 and ≥ 60 mL/min/1.73m²)
- Type of albuminuria at screening (high albuminuria, very high albuminuria)
- History of CVD (present, absent)

Persistent high albuminuria is defined as UACR of ≥ 30 mg/g (≥ 3.4 mg/mmol) but <300 mg/g (<33.9 mg/mmol) in 2 out of 3 first morning void samples. Persistent very high albuminuria is defined as UACR of ≥ 300 mg/g (≥ 33.9 mg/mmol) in 2 out of 3 first morning void samples.

Key subgroups (in addition to stratification factors)

- Sex (male, female)
- Race (white, black, Asian, other)
- Age at run-in visit (<65, ≥ 65 years)
- eGFR category at baseline (eGFR <25, 25 to <45, 45 to <60 and ≥ 60 mL/min/1.73m²)
- Type of albuminuria at baseline (normalalbuminuria (UACR <30 mg/g), high albuminuria, very high albuminuria)
- Baseline serum potassium value (\leq median and $>$ median in the FAS)
- UACR at baseline (\leq median and $>$ median in the FAS)
- Systolic blood pressure at baseline (\leq median and $>$ median in the FAS)
- Baseline BMI (<30, ≥ 30 kg/m²)
- Hemoglobin A1C ($\leq 7.5\%$ / $> 7.5\%$)
- SGLT-2 inhibitors treatment at baseline (yes, no)
- GLP-1 agonists treatment at baseline (yes, no)

Other subgroups

- Baseline serum potassium value (≤ 4.5 , > 4.5 mmol/L)

- Baseline serum potassium (by quartiles in the FAS: $\leq Q1$, $>Q1$ and $\leq Q2$, $>Q2$ and $\leq Q3$, $>Q3$)
- Baseline serum potassium value (≤ 4.8 mmol/L, >4.8 to 5.0 mmol/L, >5.0 mmol/L)
- Baseline hemoglobin A1C (by quartiles in the FAS: $\leq Q1$, $>Q1$ and $\leq Q2$, $>Q2$ and $\leq Q3$, $>Q3$)
- Baseline C-reactive protein (by quartiles in the FAS: $\leq Q1$, $>Q1$ and $\leq Q2$, $>Q2$ and $\leq Q3$, $>Q3$)
- Systolic blood pressure at baseline (<130 mmHg, 130 to <160 mmHg, and ≥ 160 mmHg)
- Age at run-in visit (18 to 44 years, 45 to 64 years, 65 to 74 years, 75 years and over)

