- Ethnicity (hispanic or latino, not hispanic or latino, not reported)
- Baseline BMI (<20 , 20 to <25 , 25 to <30 , 30 to <35 , ≥ 35 kg/m²)
- Baseline weight (<60 , 60 to <90 , ≥ 90 kg)
- eGFR category at baseline (eGFR <30 , 30 to <60 , 60 to <90 and ≥ 90 mL/min/1.73m²)
- eGFR at baseline 25 to <45 ml/min/1.73m² and baseline serum potassium value >4.5 mmol/L (yes, no)
- ACEI at baseline (yes, no)
- ARB at baseline (yes, no)
- Beta-blocker at baseline (yes, no)
- Diuretic at baseline (yes, no)
- Statins at baseline (yes, no)
- Other anti-diabetic treatment at baseline: insulin and analogues (yes, no); DPP-4 inhibitors (yes, no); biguanides (yes, no); sulfonylureas (yes, no); alpha glucosidase inhibitors (yes, no); meglitinides (yes, no); thiazolidinediones (yes, no)
- Potassium supplementation at baseline (yes, no)
- Potassium lowering agents (including binders) at baseline (yes, no)
- Potency of concomitant CYP3A4 inhibitor medication at baseline (strong, unclassified, moderate, weak, none)
- Potency of concomitant CYP3A4 inducer medication at baseline (strong, unclassified, moderate, weak, none)
- Baseline waist circumference (normal [men <94 cm, women <80 cm], increased [men 94 - 102 cm, women 80 - 88 cm], substantially increased [men >102 cm, women >88 cm])

If the result for a subgroup cannot be calculated due to a small sample size or number of events, then this subgroup will be dropped.

Individual country analyses, e.g. for Japan, required for regulatory purposes, will be included in a country-specific study SAP.

For the safety variables

- Number of subjects with hyperkalemia (treatment-emergent only)
- Number of subjects with hospitalization for hyperkalemia
- Number of subjects discontinuing study drug permanently due to hyperkalemia
- Number of subjects with hospitalization for worsening of renal function
- Number of subjects discontinuing study drug permanently due to worsening of renal function

exploratory subgroup analyses will be performed in the following selected subgroups:

- eGFR category at baseline (eGFR <25, 25 to <45, 45 to <60 and ≥ 60 mL/min/1.73m²)
- eGFR category at baseline (eGFR <30, 30 to <60, 60 to <90 and ≥ 90 mL/min/1.73m²)
- Baseline serum potassium value (≤ 4.5 , > 4.5 mmol/L)
- Baseline serum potassium value (≤ 4.8 mmol/L, > 4.8 to 5.0 mmol/L, > 5.0 mmol/L)
- Hyperkalemia (based on MLG) in medical history (yes, no)

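### Effect modification by continuous baseline measures is tested only after grouping them, which lowers power for a graded interaction in the exploratory subgroup analyses

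*SAP*

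**What the plan says.** SAP 4.5.4 calls the subgroup analyses exploratory and describes them in one sentence: "Analysis will include descriptive statistics, graphical display of estimated treatment effects with 95%-CIs in a forest plot and a statistical test for interaction". It gives no interaction model, degrees of freedom or significance level. The continuous measures appear as follows:

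- **UACR:** FAS median, plus albuminuria type at screening and at baseline.
- **Potassium:** FAS median, 4.5 mmol/L, FAS quartiles, and 4.8/5.0 mmol/L.
- **SBP:** FAS median, and 130/160 mmHg.
- **eGFR:** three classes at screening, two different four-class groupings at baseline, and a joint yes/no group with potassium.
- **HbA1c:** 7.5%, and quartiles.
- **BMI:** 30 kg/m², and five classes.
- **Age:** 65 years, and four classes.
- **CRP:** quartiles only.

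Protocol 10.3.3.6 also lists only categories. It anticipates that "differences in treatment effects may be observed according to the screening or baseline characteristics defined", and attributes this partly to differing event risk between the subgroups. Elsewhere, the mixed models in SAP 6.2.3.2 and 6.2.3.3 hold baseline-by-visit and treatment-by-visit terms only. The one continuous treatment interaction in the primary-endpoint Cox model is with log time, as a proportional-hazards check (SAP 6.2.1.2).

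**The concern.** Whether benefit changes across the range of albuminuria, kidney function, potassium or blood pressure is a question the protocol itself raises. If the change is gradual, a grouped test treats everyone in a class alike and ignores the variation within it, so a real gradient is easier to miss. Interaction tests already have limited power at this number of events. In addition, one measure can receive up to four interaction p-values that may disagree with each other, none of them uses the full scale, and the SAP does not say which represents the measure.

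What is at stake is how heterogeneity of effect is read, not the primary or secondary hypothesis tests.

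**Working it through.** **Inputs from the documents.** 1:1 randomization (Protocol 5). Event target: "The study will stop when approximately 976 primary efficacy endpoints accrue across both treatment arms" (Protocol 10.4). Cuts as listed in SAP 4.5.4.

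**Assumptions not in the documents.** Two-sided 5% for the interaction test; the modifier's distribution; a log-linear interaction and its size; group shares at fixed cuts. Event counts for the secondary endpoints are not given, so the figures below concern the primary endpoint only.

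**1. The plan's own figure.** Protocol 10.4: "A total of between 970 and 976 primary efficacy endpoint events will have 90% power to demonstrate superiority of finerenone to placebo", "at a two-sided significance level of 5.0%, assuming a 20% relative risk reduction, i.e. a true hazard ratio of 0.80". Without dilution, 4(1.960 + 1.282)²/(ln 0.80)² = 844.1, so 845 events. The protocol adds that "the hazard ratio that will be observed in the study will be different, i.e. closer to 1 due to treatment discontinuations". I let finerenone patients who stop (5% a year) revert to the placebo hazard, with 8% annual placebo events, 0.7% annual loss and uniform accrual. The event-weighted hazard ratio is then 0.812. The 33+11-month plan needs 968 events and the 41+7-month plan needs 974, each with 90.05% power. This agrees with 970 and 976, so 976 is a sound basis. (SAP 3 gives the lower end as 960; this does not matter here.)

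**2. Formula.** Let b be the log ratio of hazard ratios per SD of the modifier.

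- Continuous test: SE = 2/√976 = 0.0640; noncentrality = (976/4)b² = 244b² on 1 df.
- Grouped test: multiply the noncentrality by the share of the modifier's variance that lies between groups. An unordered test uses (groups − 1) df.
- Shares: normal median split 2/π = 0.637; uniform median split 0.75; normal quartiles 0.861.

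**3. One worked case.** Take a ratio of hazard ratios of 1.30 between the upper and lower halves of a normal modifier. The half-means differ by 2√(2/π) = 1.596 SD, so b = 0.2624/1.596 = 0.1644, or 1.18 per SD.

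- Continuous: z = 0.1644/0.0640 = 2.57, power 73%.
- Median split: SE = √(4/488 + 4/488) = 0.128; z = 0.2624/0.128 = 2.05, power 54%.

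**4. Range, normal modifier.** Power in %, losses in points against the continuous test.

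| Ratio per SD | Continuous power | Median-split power | Loss: median | Loss: quartiles, 3 df | Loss: quartile trend, 1 df | Loss: 30/70 split | Loss: four classes, 3 df |
|---|---|---|---|---|---|---|---|
| 1.10 | 31.9 | 22.1 | 9.8 | 13.4 | 3.7 | 11.5 | 15.0 |
| 1.15 | 58.8 | 41.4 | 17.4 | 22.1 | 6.2 | 20.7 | 25.8 |
| 1.20 | 81.3 | 62.3 | 19.0 | 22.5 | 6.0 | 23.3 | 27.8 |
| 1.25 | 93.6 | 79.4 | 14.2 | 15.5 | 3.8 | 18.3 | 20.7 |
| 1.30 | 98.4 | 90.5 | 7.9 | 7.8 | 1.6 | 10.9 | 11.6 |

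The 30/70 split stands in for cuts such as HbA1c 7.5% or BMI 30. The four classes (2/28/20/50%) stand in for baseline eGFR. Both sets of shares are assumed. The median-split loss peaks at 19.4 points near 1.18 per SD. It is at least 13 points only between about 1.12 and 1.26, where the continuous test has 42% to 95% power.

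**5. Other shapes.** For a uniform modifier with upper/lower-half ratios of 1.20, 1.25, 1.30 and 1.40, the median-split losses are 8.0, 10.7, 12.2 and 11.1 points. If the truth is a step of 1.30 exactly at the median of a normal modifier, the order reverses: the fitted slope is 0.2624 × 0.399 = 0.1047, z = 1.64, power 37%, against 54% for the split.

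**6. Simulation check.** Cox models with 7400 patients, 976 events, a normal prognostic modifier and 800 runs per setting gave median-split losses of 20, 23 and 16 points at 1.15, 1.20 and 1.25 (Monte Carlo error about 2 points). Type I error was about 5% for every version. The formula does not exaggerate the loss.

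**The case against.** The case on the other side is substantial.

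- **Status.** The analyses are labelled exploratory and lie outside the testing hierarchy in SAP 4.7. Categories with forest plots are a legitimate and readable choice, and the SAP separates key from other subgroups. This stands, and it limits the point to an improvement. The labels do not settle which test represents a measure: among stratification factors and key subgroups alone, albuminuria has three and eGFR two.
- **Scope.** A reader might infer that 13 to 19 points applies to every listed measure. It does not. Only UACR, potassium and SBP are median-split.
- **Shape.** Entry rules truncate the modifiers (screening potassium at most 4.8 mmol/L, SBP below 160 mmHg, UACR up to 5000 mg/g), and a bounded distribution loses less. This stands, so the lower range must be quoted too.
- **Form of the test.** A 3-df quartile test is an assumption. A 1-df trend is not excluded and would lose little.
- **Steps.** Starting dose changes at eGFR 60 and up-titration depends on potassium 4.8 mmol/L (Protocol 7.4), so step effects are plausible, and a linear term is then weaker. A reader might conclude that the continuous test should replace the grouped ones. The documents do not support that.
- **Motive.** Protocol 10.3.3.6 speaks of differences between categorical subgroups and partly of differing event risk. It does not predict a gradient in the hazard ratio, and it does not list HbA1c or BMI.

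None of these supplies a test that uses the full scale.

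**Conclusion.** The point holds as a modest, conditional one. All eight measures enter the interaction tests only in groups, and this lowers power for a graded effect.

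The size depends on assumptions the documents do not supply. At 976 events and two-sided 5%, a median split costs about 13 to 19 points for a normal modifier with a log-linear gradient of about 1.12 to 1.26 per SD. It costs about 8 to 12 points for a uniform modifier or for gradients near 1.10 or 1.30. For HbA1c, BMI, eGFR classes and quartiles, the loss runs from about 2 to 6 points (1-df quartile trend) up to about 23 to 28 points (unequal or multi-df groupings, assumed shares).

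A reader might infer that the subgroup plan is invalid or that the trial's main result is exposed. Neither follows: the grouped tests keep their type I error, carry no confirmatory claim, and are the better tests if the effect is a step at a chosen cut.

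**What to change.** In SAP 4.5.4, beside the grouped analyses already listed, add one pre-specified treatment-by-continuous-covariate test for each of log UACR, eGFR, potassium, SBP, HbA1c, BMI, age and log CRP:

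- For the primary and secondary time-to-event endpoints, fit the term with the covariate main effect in the stratified Cox model.
- For Month 4 UACR, add the same term to the ANCOVA, which already carries log baseline UACR.
- Plot the estimated hazard ratio against the covariate, with a simple non-linearity check such as a spline.
- Keep the grouped estimates, forest plots and interaction tests, and state the model and degrees of freedom of the grouped tests.

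The cost is SAP wording and one extra model per covariate for each endpoint, with no new data. The downside is that the linear term is weaker than the grouped test when the true effect is a step, which is why the grouped tests stay.

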4.6 Validity Review

The results of the validity review meetings will be documented in the validity review reports and may comprise decisions and details relevant for statistical evaluation. Any changes to the statistical analysis prompted by the results of the validity review meetings will be documented in an amendment and, if applicable, in a supplement to this SAP.

4.7 Testing procedure and multiplicity adjustment

If the decision will be to stop the study early for success (see section 4.4 for a description of the stopping rules), the final primary analyses, both for the primary and secondary efficacy endpoints, will be performed at a two-sided significance level of 0.270%. Only if both the primary and the key secondary efficacy endpoint achieve this significance level, the corresponding null hypotheses can be rejected and the remaining secondary endpoints will also be tested at a two-sided level of 0.270% according to the following hierarchy:

- Time to all-cause hospitalization
- Time to all-cause mortality
- Change in UACR from baseline to Month 4
- Time to first occurrence of the following renal composite endpoint: onset of kidney failure, a sustained decrease in eGFR of $\geq 57\%$ from baseline over at least 4 weeks or renal death

If the decision will be not to stop the study early for success, the final primary analyses will be performed as follows: A group sequential design with a single interim analysis when 2/3 of the information is available with a stopping rule of two-sided $p < 0.00270$ requires a small adjustment to the final analysis that is slightly lower than $p = 0.05$ to maintain the overall significance level at 5%. A hierarchical testing procedure will be used for the primary and secondary efficacy variables in the order mentioned below with each variable being tested at the adjusted two-sided significance level of 0.04967388, which applies for an information fraction of 2/3.

- Primary CV composite endpoint
- Key renal composite endpoint
- Remaining secondary efficacy endpoints as in the order mentioned above for a stop at the interim analysis

If the testing strategy stops at one point due to a non-significant result, the testing of the remaining secondary efficacy variables will be performed in an explorative manner only.

